4.5.1 Inclusion Criteria

- Subject is able to provide informed consent to participate in the study;
- Subject is 18 years of age or older;
- Subject has failed to respond to at least 6 months of conventional treatment including pharmacological treatment, physical therapy, epidural injections and/or radiofrequency therapy as per NICE Tag 0159;
- FBSS subjects with predominant low back pain;
- Subject has a low back and pain intensity of at least 6.0 out of 10.0 on the VAS at baseline;
- Subject is on stable pain medications with a total opioid equivalent of 120 mgs a day or less for at least 28 days prior to enrolling in this study, and is willing to stay on those medications with no dose adjustments until activation of the permanently implanted SCS device;
- Subject's medical record has been evaluated by the Investigator to ensure that the subject is a good candidate for a neurostimulation system;

Clinical Investigational Plan

- Subject is willing to cooperate with the study requirements including compliance with the regimen and completion of all office visits;
- Female candidates of child-bearing potential agree to commit to the use of an effective method of contraception (including but not limited to sterilization, barrier devices, oral contraceptives, intrauterine devices (IUDs), condoms, rhythm method, or abstinence) for the duration of the study

Subjects are not eligible for clinical study participation if they meet any of the following exclusion criteria:

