If the VAS score during either of the two trial assessments is reduced by at least 50% compared to the baseline score, the subject will be considered for permanent SCS implant. Subjects who do not experience a $\geq 50\%$ overall pain relief on either of the 2 leads will exit the study.

Subjects who underwent a successful trial ($\geq 50\%$ overall pain relief) will then be implanted with a SJM Proclaim™, Prodigy™ or Prodigy MRI™ system. The lead activated will depend on the subject's preference following the trial. If the subject has no preference; the lead placed using the anatomic midline-based technique will be activated. The subject will then be followed for 12 months to assess the long term treatment outcome. Follow up visits will occur at 3, 6 and 12 months after permanent implant. During each of these visits, subjects will rate their pain using the VAS, their quality of life using the EQ-5D, their disability using the ODI.

The total duration of the study is expected to be approximately 2 years.

The clinical study will be conducted in up to 3 centers in the E.U.

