4.4 ENDPOINTS

4.4.1 Primary Endpoint

- Changes in low back and lower limb pain between baseline and SCS trial assessments.

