4.4.2 Secondary Endpoint

- Comparison of subject preference between the 2 lead implantation techniques during the SCS trial
- Changes in low back and lower limbs pain between baseline and at 3, 6 and 12 months after permanent implant (evaluated using Visual Analog Scale (VAS) assessments)
- Changes in quality of life assessed using the EQ-5D questionnaire and in disability assessed using the Oswestry Disability Index (ODI) between baseline, trial assessments and at 3, 6 and 12 months after permanent implant
- Evaluate subject satisfaction at 3, 6 and 12 months after permanent implant

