6.4 BASELINE VISIT

Baseline screening of subjects can occur at the same visit of enrollment after the informed consent has been obtained. Subjects will be screened according to inclusion/exclusion criteria. Subjects will perform assessment of pain levels (VAS), quality of life (EQ-5D) and disability (ODI).

Subjects will be provided with a pain diary, instructed to fill it daily and return it at the SCS trial implant visit.

Clinical Investigational Plan

The following activities and assessments will be performed during baseline visit:

Timing of visit	Activities at visit	Case Report Form
Baseline	
Subject assessments of current pain levels, quality of life and disability	
• VAS Form• EQ-5D Form• ODI Form

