12.3 PASS/FAIL CRITERIA TO BE APPLIED TO THE RESULTS OF THE CLINICAL STUDY

The trial will be considered successful if significant pain relief can be obtained using burst stimulation in leads implanted using anatomical midline-based lead positioning.

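### The one scheduled pre-implant VAS both applies the low back entry cut-off and serves as the low back baseline, so regression to the mean counts as relief wherever low back change has no control

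*Combined protocol and SAP*

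**What the plan says.** - **Entry (Synopsis; 4.5.1).** Low back pain must be "at least 6.0 out of 10.0 on the VAS at baseline". No cut-off is set for lower limb pain, EQ-5D or ODI.
- **Timing (6.2 schedule; 6.4).** The schedule shows one VAS before the trial implant, at Baseline Screening. 6.4 says "Baseline screening of subjects can occur at the same visit of enrollment after the informed consent has been obtained", and its activity table describes the rating as one of current pain. No separate qualifying VAS is described.
- **Endpoints (4.4).** The primary endpoint is "Changes in low back and lower limb pain between baseline and SCS trial assessments". A secondary endpoint is "Changes in low back and lower limbs pain between baseline and at 3, 6 and 12 months after permanent implant".
- **Implant rule (4.2; 6.7).** A subject is considered for permanent implant "If the VAS score during either of the two trial assessments is reduced by at least 50% compared to the baseline score".
- **Success criterion (12.3).** "The trial will be considered successful if significant pain relief can be obtained using burst stimulation" in leads placed by the anatomical midline method. No comparator is named.
- **Diary (6.4).** "Subjects will be provided with a pain diary, instructed to fill it daily and return it at the SCS trial implant visit". No endpoint or analysis uses these pre-implant ratings, and the 6.2 schedule does not show a diary being issued at baseline.
- **Analysis (12.1).** One sentence names repeated measures ANOVA for VAS, EQ-5D and ODI. It does not define baseline or address regression to the mean.

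**The concern.** A single pain rating is a subject's usual level plus that day's deviation. A cut-off of 6.0 applied to that rating keeps people near the line who were having a bad day and drops similar people who were having a good one. Among those kept, the baseline therefore overstates usual pain on average. The next rating will be lower even if nothing has been done.

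This would not matter if the selecting reading were discarded, but here it is also the value that later low back scores are compared with. Two results depend on such a comparison with no concurrent control: low back change at 3, 6 and 12 months, and the 12.3 criterion if it is read as change from baseline with the anatomical midline lead. In both, regression to the mean would be reported as relief from stimulation.

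**Working it through.** **The plan's own figure.** 12.2 expects at least 80% trial success from about 50 enrolled: 50 × 0.80 = 40, which matches the implant target. 12.2 gives no power, effect size or VAS variance, so the inputs below are assumptions shown as ranges.

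**Inputs**
- From the documents: cut-off 6.0 on a 10-point scale; about 50 subjects in the trial phase; about 40 implanted.
- Assumed: true low back pain among candidates has mean μ of 6.5 to 7.5 and between-subject SD 1.2; day-to-day SD σw is 0.8 to 1.5, independent between visits; treatment effect zero; one-sample t-test against baseline, two-sided 0.05 (12.1 names only repeated measures ANOVA and no alpha).

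**Formula.** Let s = √(1.2² + σw²), r = 1.2²/s², a = (6 − μ)/s and c = (10 − μ)/s. With entry at 6 to 10, the expected fall with no treatment effect is

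(1 − r) × s × [φ(a) − φ(c)] / [Φ(c) − Φ(a)].

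**Middle case (μ = 7.0, σw = 1.2)**
1. s = √2.88 = 1.697; r = 1.44/2.88 = 0.50; a = −0.589; c = 1.768.
2. Fall = 0.50 × 1.697 × (0.3354 − 0.0836)/0.6836 = 0.31 points.
3. Simulation of the same model gives a fall of 0.31 and an SD of change of 1.55.
4. Noncentrality at n = 50 is (0.313/1.55) × √50 = 1.43, so the test declares relief in 29% of trials. At n = 40 it is (0.313/1.55) × √40 = 1.28, giving 24%. The nominal rate in that direction is 2.5%.

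**All cases.** Each cell gives the spurious fall in points, then the approximate false-relief rate at n = 50 and at n = 40, using the model's own SD of change.

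| μ | σw 0.8 (SD of change 1.1) | σw 1.2 (1.55) | σw 1.5 (1.9) |
|---|---|---|---|
| 6.5 | 0.25; 36%; 30% | 0.48; 57%; 47% | 0.64; 65%; 55% |
| 7.0 | 0.16; 18%; 15% | 0.31; 29%; 24% | 0.42; 35%; 29% |
| 7.5 | 0.08; 7%; 6% | 0.15; 10%; 9% | 0.21; 12%; 10% |

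**Sensitivity**
- If the SD of change were 2.5, larger than this model implies, the n = 50 rates would be about 4 to 42% (14% in the middle case).
- A different set of assumptions (mean 6 to 7.5, total SD 1.5 to 2.0, test-retest correlation 0.5 to 0.9, scores held to 0–10) gives a fall of 0.04 to 0.80 points. The false-relief rate is 7 to 88% at n = 50. The middle case (mean 7, SD 2, correlation 0.7) again gives 0.31 points, with 34%.
- The n = 40 figures apply only the entry selection. They do not model the further selection of implanted subjects by the 50% rule.

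**What is not affected.** In the second set of simulations the mean difference between leads stays within 0.01 point of zero, and a test of it rejects in 4.3 to 5.6% of trials. The same baseline is subtracted from both leads and drops out.

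**After the change.** With a second pre-implant rating, not used for selection, as the baseline, the spurious change is within 0.01 point of zero in every scenario of both models.

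**The case against.** The primary objective in 4.3.1 compares the two leads within subject, and that contrast is free of this bias. A reader might infer that the primary comparison is compromised; it is not. A reader might also infer that every change-from-baseline endpoint is inflated. The documents do not support that: EQ-5D and ODI have their own baselines without a cut-off, and the threshold does not apply to lower limb pain. These could be affected only indirectly, through correlation with low back VAS.

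The size is also modest. The middle-case fall of 0.31 is about 4% of a mean retained baseline of 7.6, whereas the 50% rule requires at least 3 points from a baseline of 6. In the second set of simulations, regression to the mean alone takes 0 to 4.1% of subjects past 50% at one visit and 0 to 7.6% at either of two, so the implant rule is little disturbed. This is a declared feasibility study, and 6.4 already provides for daily pre-implant ratings.

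All of this stands and limits the scope. It does not remove the point. The diary is not named as a baseline anywhere, the 12- month results have no control, and a test for any significant fall from baseline is sensitive to a shift of a few tenths of a point at these sample sizes.

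**Conclusion.** The point holds for uncontrolled low back VAS change: the 3, 6 and 12 month low back results, the per-lead change from baseline at the trial assessments, and the 12.3 criterion when read as change from baseline. Under the assumptions above, the spurious fall is 0.08 to 0.64 points (0.31 in the middle case). False relief is declared in about 7 to 65% of trials at n = 50 (29%) and 6 to 55% at n = 40 (24%), against 2.5%. These sizes rest on an assumed mean, variance and test, none of which the documents supply. The direction of the bias needs only that some day-to-day variation exists and that candidates fall on both sides of the cut-off.

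A reader might go further and conclude that the effect size passed to a later trial will be inflated. 12.2 says the study should yield estimates of the effect size but not which effect. If it means the difference between leads, that estimate is not biased by this mechanism. The change is worth making because it is cheap; the randomized comparison does not depend on it.

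**What to change.** 1. In 4.4.1 and 4.4.2, define the endpoint baseline for low back pain as a pre-implant reading to which no cut-off is applied. Two options:
   - the mean of the daily pre-implant diary in 6.4, over a stated window that starts after the day of the qualifying VAS, compared with the corresponding diary means in the trial and follow-up periods; or
   - a second VAS on a later day before the trial implant, compared with the visit VAS scores.
2. Align 6.4 and the 6.2 schedule with the choice. If the diary is used, show it issued at baseline and collected at the trial implant visit, and confirm that its form rates low back pain separately (the forms are held under separate cover).
3. State in 4.2 and 6.7 that the 50% implant rule keeps its present reference reading, so that the word baseline has one meaning in each place. The rule itself is not changed.
4. State in 12.3 what the relief is compared with.

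The cost is a few sentences and at most one extra short rating. Reported low back change scores will be slightly smaller. The change removes the selection effect only to the extent that day-to-day deviations do not persist to the second reading. It does not address placebo response, natural course or the absence of a control after implant.

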4.5.2 Exclusion Criteria

- Subjects with significant scoliosis even if surgically corrected;
- Subject is currently participating in a clinical investigation that includes an active treatment arm;
- Subject has been implanted with or participated in a trial period for a neurostimulation system;
- Subject has an infusion pump;
- Subject has evidence of an active disruptive psychological or psychiatric disorder as determined as per standard of care;
- Subject has a current diagnosis of a coagulation disorder, bleeding diathesis, progressive peripheral vascular disease or uncontrolled diabetes mellitus;
- Subject has a current diagnosis of a progressive neurological disease as determined by the Investigator;
- Subject is immunocompromised;
- Subject has an existing medical condition that is likely to require repetitive MRI evaluation in the future (i.e. epilepsy, stroke, multiple sclerosis, acoustic neuroma, tumor);
- Subject has history of cancer requiring active treatment in the last 12 months;
- Subject has an existing medical condition that is likely to require the use of diathermy in the future;
- Subject has documented history of allergic response to titanium or silicone;
- Subject has a documented history of substance abuse (narcotics, alcohol, etc.) or substance dependency in the 6 months prior to baseline data collection;
- Female candidates of child bearing potential that are pregnant (confirmed by positive urine/blood pregnancy test).

Clinical Investigational Plan

4.6 SUBJECT POPULATION

The study population consists of FBSS patients with a diagnosis of chronic low back pain accompanied by lower limb pain, and eligible for a SCS trial.

4.6.1 Subject Screening

All subjects presenting at the investigational site can be screened by a member of the investigational team previously trained on the CIP and delegated to do so.

Subjects who do not meet the inclusion/exclusion criteria will not be eligible to participate in this study.

Subjects meeting the inclusion/exclusion criteria will be fully informed about the study and asked to participate in the study. In case the subject agrees, a duly signed and dated Patient Informed Consent will be obtained.

4.6.2 Point of Enrollment

Subjects are considered enrolled in the study from the moment the subject has provided written Patient Informed Consent, has been screened for inclusion/exclusion criteria and his/her enrollment form has been completed. (Refer to section 4.7 for the Informed Consent Process).

4.7 INFORMED CONSENT PROCESS

4.7.1 General process

Prior to enrolling in the clinical study and conducting study-specific procedures, all subjects will be consented, as required by applicable regulations and the center's IRB/EC. Informed consent must be obtained from each subject prior to any study related procedures. The consent form must be signed and dated by the subject and by the person obtaining the consent.

The principal investigator or his/her authorized designee will conduct the Informed Consent Process. This process will include a verbal discussion with the subject on all aspects of the clinical study that are relevant to the subject's decision to participate in the clinical study.

The subject shall be provided with the informed consent form that is written in a language that is understandable to the subject and has been approved by the center's IRB/EC. Failure to obtain informed consent from a subject prior to study enrollment should be reported to St. Jude Medical within 5 working days and to the reviewing center's IRB/EC/ consistent with the center's IRB/EC reporting requirements.

Clinical Investigational Plan

5.0 DEVICE UNDER INVESTIGATION

5.1 DEVICE DESCRIPTION

In this study, the SJM Invisible trial system and the Proclaim™, Prodigy™ or Prodigy MRI™ neurostimulation system will be used.

Table 1: Description of Proposed Devices

Device Component	Model/Type	Investigational or Market Released
SJM Invisible trial external pulse generator (EPG)	3599 (Base), 3032 (Header)	Released
SJM Invisible trial Clinician Programmer	3870, 3872	Released
SJM Invisible trial Patient Controller	3871, 3873	Released
SJM Lead extension	338X	Released
SJM Proclaim internal pulse generator (IPG)	3660, 3662	Released
SJM Prodigy IPG	3799	Released
SJM Prodigy MRI IPG	3772	Released
SJM Clinician Programmer App	3874	Released
SJM Patient Controller App	3875	Released
SJM Rapid programmer System	3831,3382	Released
Prodigy MRI Patient programmer	3855	Released
Prodigy MRI charger	3730	Released
SJM Octrode™ lead	318X	Released
SJM Cinch™ Lead Anchor	1194	Released
SJM Swift-Lock™ Anchor	1192	Released

- **SJM Invisible trial™ external pulse generator (EPG):** a 16 channels, software controlled, battery powered, external stimulator that generates the electrical pulses to be used during the trial phase of the study
- **SJM Invisible trial Clinician Programmer:** software compatible with iOS™ App 8.1 or later to be used on iPad mini™; enables the clinician to program the SJM Invisible trial EPG
- **SJM Invisible trial Patient Controller:** software compatible with iOS™ App 8.1 or later to be used on iPad touch™; enables patient-controlled therapy adjustment of the SJM Invisible trial EPG
- **SJM Percutaneous trial lead:** sterile stimulating electrode placed in the epidural space of the spinal cord and connected to the EPG

Clinical Investigational Plan

- **SJM Lead extension:** sterile extension that connects the pulse generator to the stimulating electrode
- **SJM Proclaim™ internal pulse generator (IPG):** a 16 channels, software controlled, battery powered, internal stimulator to be used during the follow up phase of the study that generates the electrical pulses
- **SJM Prodigy IPG:** a 16 channels, software controlled, rechargeable battery powered, internal stimulator to be used during the follow up phase of the study that generates the electrical pulses
- **SJM Prodigy MRI™ IPG:** a 16 channels, software controlled, rechargeable battery powered, internal stimulator to be used during the follow up phase of the study that generates the electrical pulses
- **SJM Clinician Programmer App:** software compatible with iOS™ App 8.3 or later to be used on iPad mini™; enables the clinician to program the Proclaim IPG
- **SJM Patient Controller App:** : software compatible with iOS™ App 8.1 or later to be used on iPad touch™; enables patient-controlled therapy adjustment of the Proclaim IPG
- **SJM Rapid Programmer™ system:** device designed to be used by the clinician to program the Prodigy MRI™ IPG
- **SJM Prodigy MRI™ Patient Programmer:** device designed to enable patient-controlled adjustment of the Prodigy MRI™ IPG
- **SJM Prodigy MRI™ Recharger:** provides the capability to recharge the Prodigy MRI™ battery
- **SJM Octrode™ lead:** sterile stimulating electrode that placed in the epidural space of the spinal cord and connected to the Proclaim IPG
- **SJM Cinch™ Lead Anchor:** securing device designed to reduce lead migration and breakage
- **SJM Swift-Lock™ Anchor:** securing device designed to reduce lead migration and breakage

5.2 DEVICE ACCOUNTABILITY (if applicable)

[figure not shown]
Device accountability is not required in post market studies.

Clinical Investigational Plan

6.0 PROCEDURES

6.1 STUDY FLOW CHART

AM lead: lead implanted using Anatomical Midline-based positioning

PM lead: lead implanted using Paresthesia Mapping-based positioning

Figure 3: Flow Chart

Clinical Investigational Plan

6.2 PROCEDURES

The clinical study will be conducted in accordance with the CIP. All parties participating in the conduct of the clinical study will be qualified by education, training, or experience to perform their tasks and this training will be documented appropriately.

The clinical study will not commence until St. Jude Medical receives written approval from the IRB/EC and relevant regulatory authorities and all required documents have been collected from the site(s).

Table 1: List of all study specific activities/procedures

Visit Study Activity	Enrollment	Baseline Screening	SCS Trial	Trial Assessment 1	Trial assessment 2	SCS Implant procedure	Activation	Follow up Visits*
Informed Consent Process	X							
Inclusion/Exclusion Criteria Screening	X							
VAS assessment		X		X	X			X
EQ-5D questionnaire		X		X	X			X
ODI questionnaire		X		X	X			X
Provide pain diary			X	X			X	X
Collect pain diary				X	X			X
Subject Preference questionnaire						X		
Trial leads implant			X					
EPG programming			X	X				
Permanent implant							X	
IPG Programming								X
Subject Satisfaction questionnaire								X

* Follow up visit assessments will be performed after activation visit at weeks 12 (84±7 days), 26 (182±7 days), and 52 (365±7 days).

6.3 ENROLLMENT VISIT

The following enrollment activities are performed after the subject has been screened and must occur before any study procedure/visit.

- The principal or delegated study personnel are responsible for screening all potential subjects to determine subject eligibility for the study

Clinical Investigational Plan

- Record enrollment information (name of the study, date of consent and Inclusion/exclusion information) in the hospital records and complete and submit the Enrollment form in a timely manner (recommended within 5 days)
- Notification of enrollment to the sponsor will take place only when the sponsor receives the enrollment form

NOTE: As soon as the subject signs the Patient Informed Consent, adverse events need to be reported according to the guidelines mentioned in section 8.

If a subject does not meet all inclusion criteria or meets any of the exclusion criteria, the subject cannot participate in the study and cannot be enrolled.

In case the subject was already consented to participate in the study, but does not meet inclusion/exclusion criteria, the following actions will be taken.

If study procedure/device implant has not occurred:

- Document enrollment information (name of the study, date of consent and inclusion/exclusion) in the hospital records; complete the Enrollment and Withdrawal Forms. The form must be authorized / approved by the principal or delegated investigator.
 - Inform the subject about the withdrawal.
 - The EC/IRB and CA should be notified appropriately about any deviations with regards to obtaining the informed consent.

If study procedure/device implant has occurred:

- Document enrollment information (name of the study, date of consent and inclusion/exclusion) in the hospital records; complete the Enrollment and Withdrawal Forms. The form must be authorized / approved by the principal or delegated investigator.
 - Complete study deviation for inclusion/exclusion not met
 - The EC/IRB and CA should be notified appropriately about any deviations with regards to obtaining the informed consent.

The following activities and assessments will be performed during enrollment:

Timing of visit	Activities at visit	Case Report Form
Enrollment	
• Subject signs informed consent• Subject is screened for inclusion/exclusion criteria• Subject is enrolled	
• Inclusion/Exclusion Form• Enrollment Form

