6.15 CRITERIA AND PROCEDURES FOR SUBJECT WITHDRAWAL OR DISCONTINUATION

Subjects must be informed about their right to withdraw from the study at any time and for any reason without sanction, penalty or loss of benefits to which the subject is otherwise entitled and withdrawal from the study will not jeopardize their future medical care or relationship with the investigator. Subjects will be asked to specify the reason for the termination, but have the right not to answer.

The investigator may decide to withdraw a subject from the study at any time with reasonable rationale. The subject's future care will not be influenced by a decision, voluntary or otherwise, to withdraw from the study. All reasonable efforts should be made to retain the subject in the clinical study until completion of the study.

Reasons for subject's withdrawal include, but are not limited to:

- Subject refuses to continue participating in the study
- Subject does not meet the inclusion/exclusion criteria and does not require additional follow-up for safety reasons.
- Subject is deceased (cause must be documented)
- Subject's non-compliance
- Subject's participation is terminated by the PI or investigator, although the subject consented, since participation is no longer medically appropriate

Clinical Investigational Plan

- Subject is 'lost to follow up': Subject does not adhere to the scheduled follow up visits but has not explicitly requested to be withdrawn from the clinical study. (This does not apply to missed visits). Site personnel should at all times make all reasonable efforts to locate and communicate with the subject in order to achieve subject compliance to the scheduled follow up visits:
 1. A subject will be considered 'Lost to Follow Up' after a minimum of 2 phone calls of a physician or delegate at the investigational site to the subject or contact. These 2 phone calls need to be documented in the subject's hospital records.
 2. If these attempts are unsuccessful, a letter should be sent to the subject's last known address or general practitioner (GP) and a copy of this letter should be maintained in the subject's hospital records.

Note: If a subject misses one or more of the scheduled follow up visits (inclusive of the assigned visit windows), this will be considered as a missed visit. The subject may therefore still return for subsequent visits and will not be excluded from the study.

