8.1.5 Serious Adverse Device Effect (SADE)

Adverse device effect that has resulted in any of the consequences characteristic of a serious adverse event.

1. Unanticipated Serious Adverse Device Effect (USADE) [applicable to studies following ISO 14155]

A serious adverse device effect which by its nature, incidence, severity or outcome has not been identified in the current version of the risk analysis report.

2. UADE [applicable to investigational studies following FDA regulations]

As defined in 21 CFR §812.3, unanticipated adverse device effects (UADE) are defined as any serious adverse effect on health or safety or any life-threatening problem or death caused by, or associated with, a device, if that effect, problem, or death was not previously identified in nature, severity, or degree of incidence in the clinical investigational plan or application (including a supplementary plan or application), or any other unanticipated serious problem associated with a device that relates to the rights, safety, or welfare of subjects.

If an unanticipated adverse device effect occurs, the investigator must notify St. Jude Medical and the IRB/MEC immediately, but no later than 10 working days of the investigator's knowledge of the event, as required by 21 CFR §812.150. St. Jude Medical will take any steps necessary to investigate the event, and will be responsible for notifying FDA and all other participating IRBs/MECs and investigators.

Clinical Investigational Plan

3. Anticipated Serious Adverse Device Effect (ASADE)

A serious adverse device effect which by its nature, incidence, severity or outcome has been previously identified in the risk analysis report.

8.2 PROCEDURE FOR ASSESSING, RECORDING, AND REPORTING ADVERSE EVENTS, DEVICE DEFICIENCIES/COMPLAINTS, ADVERSE DEVICE EFFECTS, SERIOUS ADVERSE EVENTS, AND SERIOUS ADVERSE DEVICE EFFECTS:

Safety surveillance within this study and the safety reporting both performed by the investigator, starts as soon as the subject is enrolled in this study (date of signature of the informed consent). The safety surveillance and the safety reporting will continue until the last investigational visit has been performed, the subject is deceased, the subject/investigator concludes his participation into the study or the subject/investigator withdraws the subject from the study, except as otherwise specified in the CIP.

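### Section 6.3 orders withdrawal of subjects found ineligible after implant without the safety condition in 6.15, so reporting of new adverse events stops and randomised subjects can lose later data

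*Combined protocol and SAP*

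**What the plan says.** Section 6.3 deals with a subject who has consented but does not meet the criteria, and splits on whether the procedure or implant has taken place. Under "If study procedure/device implant has occurred", the site must "complete the Enrollment and Withdrawal Forms", and "The form must be authorized / approved by the principal or delegated investigator". The instruction on these forms is the same in the non-implanted branch. The implanted branch differs in two ways: it adds "Complete study deviation for inclusion/exclusion not met", and it leaves out the instruction to tell the subject about the withdrawal.

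Section 6.15 introduces its list with "Reasons for subject's withdrawal include, but are not limited to". The relevant entry is "Subject does not meet the inclusion/exclusion criteria and does not require additional follow-up for safety reasons". The same section asks sites to make all reasonable efforts to keep subjects in the study to completion. It calls for a final study visit, but the list of evaluations for that visit is an unfilled template line. Its explicit follow-up after withdrawal concerns subjects withdrawn because of an adverse event.

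Section 8.2 runs safety surveillance and reporting from consent until one of several end points. One of these is that "the subject/investigator withdraws the subject from the study", subject to any exception elsewhere in the protocol. It also requires adverse events to be monitored until adequately resolved.

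Randomisation to lead sequence is described in section 6.5, with the trial implant. Section 12.1 names a repeated measures ANOVA and defines no analysis set and no rule for missing data.

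**The concern.** A site with an implanted subject who turns out to be ineligible has two instructions. Section 6.3 says to withdraw, without qualification. The entry in 6.15 asks first whether safety follow-up is still needed. If the site follows 6.3, then 8.2 closes the reporting window.

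These are subjects whom the plan itself regards as at risk. Section 7.2 says the criteria exist to exclude people for whom use involves unreasonable risk. The exclusions in 4.5.2 include coagulation disorder, bleeding diathesis and immunocompromise, and the anticipated events in 3.3 include epidural haemorrhage and infection. Reporting of new events would stop in the group where the plan has most reason to want it.

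The second issue is the comparison. Because 6.3 has no cut-off at randomisation, it can act as a post-randomisation exclusion approved at the site. Section 12 says nothing about how such subjects are analysed.

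**Working it through.** **The plan's own figure.** Section 12.2 expects at least 80% trial success among about 50 subjects: 50 × 0.80 = 40 permanent implants. This reproduces. The plan states no power, alpha or standard deviation, and the present point does not rest on the 40.

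**The texts side by side.**

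| Question | 6.3, implanted branch | 6.15 | 8.2 |
|---|---|---|---|
| Is the ineligible subject withdrawn? | Yes, no condition | Listed ground only if no safety follow-up is needed; list not exhaustive | – |
| Is the subject told? | Not stated (stated in the other branch) | – | – |
| New events after withdrawal? | – | No rule for this case; final visit has no content | Surveillance ends, unless the protocol says otherwise |
| Events already open? | – | Followed if they caused the withdrawal | Monitored to resolution |

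The protocol provides exceptions for an adverse event that caused the withdrawal and for events already open. Neither covers a new event after withdrawal for ineligibility.

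**What is lost, by time of removal** (sections 6.5 to 6.7 and 6.10).

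| Removal | On-treatment outcome collected at scheduled visits | Data lost |
|---|---|---|
| Trial implant to before Trial Assessment 1 | None: the diary is with the subject, and the first on-treatment VAS is at that visit | Both lead measurements |
| Trial Assessment 1 to before Trial Assessment 2 | First lead only | Second lead measurement, hence the paired contrast |
| After Trial Assessment 2 | Both leads | Whichever of the 3, 6 and 12 month assessments remain |

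Removal that is both informed by a collected result and costly to the paired contrast is therefore confined mainly to the two weeks of phase 2, and it can use the result for one lead only.

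**Precision.** The documents give no rate of late-found ineligibility. Assume 2% to 10% of 50 subjects: 0.02 × 50 = 1 and 0.10 × 50 = 5. If k subjects lose their contrast, the variance of the mean lead difference is multiplied by 50/(50 − k):
- k = 1: 50/49 = 1.02
- k = 5: 50/45 = 1.11

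Assuming two-sided alpha 0.05 and 80% power, the detectable standardised paired difference is (1.960 + 0.842)/√n. It is 0.396 with 50 pairs and 0.418 with 45. These figures are an upper range, because a subject found ineligible after Trial Assessment 2 keeps the contrast.

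**The case against.** **Sections 6.3 and 6.15 can be read together.** The 6.15 list is not exhaustive, and the section separately lets the investigator withdraw a subject at any time with reasonable rationale. On that reading 6.3 names the forms and 6.15 supplies the condition. This stands to the extent that a reader who infers a strict contradiction goes too far. It does not remove the problem, since 6.3 carries no condition and no cross-reference.

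**Safety reporting does not simply end.** A reader might infer that device events in these subjects fall outside reporting altogether. The documents do not support that: 8.2 allows exceptions, open events are monitored to resolution, and 6.15 calls for a final visit. The gap is limited to events that begin after withdrawal. The final visit is a weak backstop because its content is blank. The documents also do not say whether hardware stays in place in such a subject.

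**The bias route is narrow.** A reader might infer that sites can use this rule to drop unfavourable lead comparisons. The visit schedule does not support it. No on-treatment outcome is collected before Trial Assessment 1, both lead measurements exist once Trial Assessment 2 is done, and nothing in the plan discards recorded data. Simulating the deletion of the 1 to 5 least favourable of 50 null differences raises type I error to between about 7% and 33%. That calculation needs complete pairs to be thrown away, so it does not describe this rule. Knowledge of the active lead is also not settled: the synopsis says double-blinded and 4.2 says single-blinded, although 6.5 programmes the two leads differently, so whoever programmes will know.

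**The numbers are small and partly replaceable.** Enrolment continues until 40 permanent implants, so a subject lost before that implant can be replaced. A variance increase of at most 11% matters little in a feasibility study without a power calculation. This stands for precision. Replacement does not restore safety reporting for the subject who was withdrawn.

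**Conclusion.** The point holds in limited form and should be corrected. Section 6.3 requires withdrawal after implant without the safety condition in 6.15 and without informing the subject. Together with 8.2, this stops the reporting of new adverse events in subjects who have had leads or a generator placed. That is the main consequence, and it follows from the text without any assumed rate.

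For the lead comparison, the rule can remove randomised subjects, and removal before Trial Assessment 2 costs the paired contrast. Selection informed by a collected result is possible mainly in phase 2 and for one lead only; no amount of bias can be put on it from the documents. The loss of precision is small, a factor of 1.02 to 1.11 in variance, on the assumption that 1 to 5 of 50 subjects are lost before both measurements are taken. Later removal leaves the primary contrast intact and costs follow-up data.

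**What to change.** **Sections 6.3 and 6.15.** Reconcile them. In the implanted branch, replace the automatic Withdrawal Form with the Enrollment and Deviation forms and restore the step of informing the subject. State that safety reporting under section 8 and scheduled data collection continue unless the subject declines or the 6.15 condition is documented. Fill in the content of the final study visit.

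**Section 12.** State that all randomised subjects with available data are analysed by assigned sequence, with a sensitivity analysis leaving out those found ineligible. A conventional repeated measures ANOVA drops a subject with one period missing, so 12.1 should also say how incomplete pairs enter the analysis.

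**Cost.** The change is wording in 6.3 and 6.15 and a short analysis-set paragraph in section 12. It adds no visits, since these are already scheduled. The small downside is that a few ineligible subjects stay in the main analysis, and the sensitivity analysis shows their influence. Decisions on stimulation or hardware in such a subject are outside this change.
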